18. DATA MONITORING PLAN

The Principal Investigator and his study staff will monitor all data accrual. In addition a data monitor will visit the study site during the study and review the progress of the clinical trial including safety data and ensure as possible that it is conducted, recorded, and reported in accordance with the protocol, Good Clinical Practice (GCP), and the applicable regulatory requirement(s). A written report form will be issued after each monitoring visit (including initiation and close out visits). The monitoring visit report will include a summary of what the monitor reviewed and the monitor's statements concerning the significant findings/facts, deviations and deficiencies, conclusions, actions taken or to be taken and/or actions recommended to secure compliance. The investigator/institution should provide direct access to source data/documents for trial-related monitoring and auditing, IRB/IEC review and inspection by the appropriate regulatory authority/ies. Remote initiation visit/ data monitoring/ close out visits are optional in case on site visits are not done.

NOTE: e-Source may be used.

Verification during monitoring visit will include:

- 1. That the investigator has adequate qualifications and resources and remains adequate throughout the trial period, that facility, including laboratories, equipment, and staff, are adequate to safely and properly conduct the trial and remain adequate throughout the trial period.
- 2. Verifying for the investigational product(s):
 - a. That storage conditions are acceptable.
 - b. That the investigational product(s) are supplied only to subjects who are eligible to receive it according to protocol and no other use is being done with the Vibrant devices.
 - c. That the receipt, use, and return of the investigational product(s) at site are controlled and documented adequately and that supplies delivery notes are confirmed upon reception throughout the trial.
 - d. That the unused investigational product(s) at sites will be returned.
- 3. Verifying that the investigator follows the approved protocol and all approved amendment(s), if any.
- 4. Verifying that written informed consent was obtained before each subject's participation in the trial.

Doc No: 280CLD Rev: 01 Date: 24 May 2021

Page 76 of 103

- 5. Ensuring that the investigator receives the current Investigator's Brochure, all documents, and all trial supplies needed to conduct the trial properly and to comply with the applicable regulatory requirement(s).
- 6. Ensuring that the investigator and the investigator's trial staff are adequately informed about the trial.
- 7. Verifying that the investigator and the investigator's trial staff are performing the specified trial functions, in accordance with the protocol and any other written agreements, and have not delegated these functions to unauthorized individuals.
- 8. Verifying that the investigator is enrolling only eligible subjects and at sufficient recruitment rate.
- 9. Verifying that source documents and other trial records are accurate, complete, kept up-to-date and maintained.
- 10. Verifying that the investigator provides all the required reports, notifications, applications, and submissions, and that these documents are accurate, complete, timely, legible, dated, and identify the trial.
- 11. Checking the accuracy and completeness of the CRF entries, source documents and other trial-related records against each other.
- 12. The data required by the protocol are reported accurately on the CRFs and are consistent with the source documents.
- 13. Adverse events, concomitant medications and intercurrent illnesses are reported in accordance with the protocol on the CRFs.
- 14. Visits that the subjects fail to make, tests that are not conducted, and examinations that are not performed are clearly reported as such on the CRFs.
- 15. All withdrawals and dropouts of enrolled subjects from the trial are reported and explained on the CRFs.
- 16. Verifying that the investigator had answered all of the queries that came up from inspection of the CRFs or other trial material.
- 17. That the investigator is maintaining the essential documents.
- 18. Verifying that deviations from the protocol, SOPs, GCP, and the applicable regulatory requirements are reported by the investigator to the IRB/IEC and that appropriate actions were taken to prevent recurrence of the detected deviations.

Should there be an unexpected number of device failures or related complications that increase the risks to the participants, or critical efficacy endpoints at intervals that are not satisfying, the study will be halted and analysis performed to determine whether to continue, modify the protocol, or close the study.

19. **DATA CONFIDENTIALITY**

Doc No: 280CLD Rev: 01 Date: 24 May 2021

Page 77 of 103

Each subject will be identified by his/ her initials and a unique subject identification number. Source data will be stored with source documents. The Investigator Site Files (ISF) will be held in a secure area. The subject's name and personal data will remain confidential and will not be published in any way. However, the sponsor's monitor or representative and regulatory representatives, auditors and inspectors may have access to medical files in order to verify authenticity of data collected. For the purpose of remote data monitoring sites will upload the source documents into a secured platform which is CFR part 11 compliant.

20. **FUNDING**

The study is funded by Vibrant Ltd.

ETHICS 21.

Prior to study initiation the site shall obtain EC or IRB approval of the study. A copy of the written EC approval must be provided to the sponsor prior to the start of the study.

Any changes in the study protocol, informed consent forms, or investigator must be re-approved by the EC or IRB and the approval documented. All subjects screened in the study will provide their consent prior to entering the study. An informed consent form shall be signed and dated by the subject. The investigator will retain the forms as part of the study records.

This study will be executed in accordance with the Declaration of Helsinki, in agreement with the guidelines for conducting a clinical investigation in accordance with the principles of ICH GCP outlined in the E6 document. By signing the present protocol, the investigator commits to carry it out in accordance with local legal requirements.

Other investigator responsibilities relative to the EC/IRB include the following:

- 1. During the conduct of the study, the investigator will submit progress reports to the EC/IRB as required, and request re-review and approval of the study at least once a year;
- 2. The investigator will report immediately to the EC/IRB of any unexpected serious adverse events that occur during the study, and provide the sponsor with a copy of the correspondence;

Doc No: 280CLD Rev: 01

Date: 24 May 2021

Page 78 of 103

- 3. If the sponsor notifies about serious adverse events reported in other studies using this device, the investigator must report that information to the EC/IRB;
- 4. As required, the investigator must obtain approval from the EC for protocol amendments and for revisions to the consent form or subject recruitment advertisements;
- 5. The investigator should provide the EC/IRB with any other information it requests before or during conduct the study;
- 6. The investigator must maintain a file of study-related information that includes all correspondence with the EC/IRB;
- 7. The investigator must notify EC/IRB when study is completed (i.e. after the last study visit of the final study subject);
- 8. After study completion (within 12 months is recommended) the investigator should provide the EC/IRB with a final report on the study. The recommended components of a final report are as follows; dates of study start and completion, number of subjects enrolled/treated, number of subjects who discontinued participation early and reason why, itemization and discussion of any serious adverse event.

Progress reports and Final reports might be submitted to EC/IRB by the Sponsor (on behalf of the investigator)

22. INFORMED CONSENT

Written informed consent must be obtained from each study subject. The subject will be asked to read the informed consent form and to sign the form to indicate consent to participate in the study.

The investigator will explain carefully to the subject the research nature of the study. The scope and aims of the research will be described together with known or foreseeable benefits, risks and discomforts that subjects may experience. Appropriate alternative treatments will be discussed so that the subject may determine whether or not he or she wishes to participate in the study. The subject must understand that throughout the study his or her participation remains voluntary and protected by the Declaration of Helsinki. The investigator is responsible for obtaining written (or witnessed) informed consent from potential subjects prior to study entry. The task of obtaining informed consent can be delegated, per PI discretion. Subjects will be given time to read the informed consent and ask any questions before being asked to sign the form. The informed consent (approved by the sponsor and the Ethics Committee) must be signed and dated by the subject and the investigator (or investigator's designee). One copy of the signed consent will be given to the subject, a second copy will be sent to the referral investigator and the original will be retained by the investigator. Subject should be identified during screening visit by driving license or any other identity card.

Subjects may withdraw their consent to participate in the study at any time without prejudice. The investigator may withdraw a subject if, in his clinical judgment, it is in the best interest of the subject or if the subject cannot comply with the protocol. Attempts should be made to complete any examinations and the sponsor must be notified of all withdrawals.

Should a protocol amendment be made, the subject's consent form may be revised to reflect the changes of the protocol. It is the responsibility of the investigator to ensure that an amended informed consent is approved or reviewed by the EC/IRB, and that it is signed by all subjects subsequently entered in the study and those currently in the study, if affected by the amendment.

23. REGULATORY AND HEALTH AUTHORITY AUDITS

The European Union's authorities and/or the Food and Drug Administration (FDA) and/or the local state health authorities may request access to all study records, including source documents for inspection. The investigator and hospital staff are requested to cooperate with these audits. The investigator must notify the sponsor of any health authority audit as soon as notification of such audit is made. A representative or designee of the sponsor may also conduct similar audits and may be present during health authority audit.

24. ELECTRONIC REPORTING OF DATA

All medical data in this trial are to be recorded directly in the EDC (Electronic Data Capture) system. Documentation on paper will be restricted to exceptional circumstances only.

The investigator must ensure the accuracy, completeness and timeliness (and legibility in case of documentation on paper) of data.

Sites will get trained on how to access and use the EDC and will be foreseen with a personal user login and password. Subjects will access and complete their diaries online via a website specifically created for the purposes of the study. Subjects will be trained on how to access and use this website and will be foreseen with a personal user login and password.

Doc No: 280CLD

Rev: 01 Date: 24 May 2021

Page 80 of 103

25. RECORD RETENTION

It is required that a copy of all records (e.g., informed consent documents, source documents, safety reports, study device dispensing record, etc.) which support case report forms for this study, be retained in the files of the responsible investigator for a minimum of fifteen (15) years following notification by the sponsor that all investigations (not merely the investigator's portion) are completed, terminated and/or discontinued. If the principal investigator retires, relocates, or for other reasons withdraws from the responsibility of keeping the study records, custody must be transferred to a person who will accept the responsibility. Vibrant Ltd. must be notified in writing of the name and address of the new custodian.

26. PROTOCOL MODIFICATIONS

An amendment to the protocol may be proposed by an investigator or the sponsor. The amendment will be prepared and approved by the sponsor according to the sponsor's relevant SOP. The amendment must be submitted to the EC/IRB. When applicable, the amendment's implementation will take place only once approved by the EC/IRB.

If for any unexpected reasons, there is any requirement to deviate from the treatments stated above, the protocol deviation should be discussed in advance with a Vibrant Ltd. representative.

27. PUBLICATION POLICY

All information concerning this study that was not previously published is considered confidential information. This confidential information shall remain the sole property of Vibrant Ltd.; it shall not be disclosed to others without written consent of Vibrant Ltd. and shall not be used except in the performance of this study.

Any investigator involved with this study is obligated to provide the Sponsor with complete test results and all data derived from the study.

28. SUBJECT / STUDY DISCONTINUATION

Page 81 of 103

Subjects should be removed from the study whenever considered necessary for their welfare or when the subject expresses a desire to withdraw from the study. Non-compliance with the protocol, the occurrence of a Serious Adverse Event or any medical condition that, in the opinion of the investigator, warrants discontinuation from the study for the safety of the subject, may necessitate discontinuing a subject. If a subject is discontinued, the reason must be entered on the case report form and signed by the investigator. In case of any questionable situation, the study monitor or Vibrant Ltd. personnel should be consulted. When a subject is removed from the study as a result of Serious Adverse Event, a final physical examination must be performed. Subjects removed from the study because of an adverse event will be followed-up until the adverse event has been resolved.

In the case that the occurrence of adverse events is greater than anticipated, the clinical investigation will be suspended; in such a case, a safety committee will be arranged to decide if the study could be continued. The Ethics Committee will be notified and the results of the safety committee discussions will be brought for the EC/IRB review and decision.

Early termination could be a result of:

- 1. Withdrawal of informed consent by the subject.
- 2. Subjects who after inclusion develop medical diseases which may affect the function and interpretation of study results.
- 3. Serious protocol deviation.
- 4. Non-compliance with medical device administration or study procedures as determined by the sponsor.
- 5. Change in subject's condition.
- 6. Subject is Lost to follow-up.
- 7. Confirmed pregnancy.
- 8. Regulatory authorities stop the trial.

During the study, subjects exiting the trial will be replaced with new subjects, up to 10%

Site staff should set an early termination visit as soon as they become aware of subject's discontinuation. During this visit, any remaining study supplies should be collected and accountability should be conducted if applicable. 'End of study' from should be completed in source documents and any other relevant information should be documented (for example, in case of AE).

Doc No: 280CLD

Rev: 01 Date: 24 May 2021

Page 82 of 103

Vibrant Ltd., reserves the right to discontinue any study for administrative reasons at any time, such as, but not limited to a decision to discontinue further clinical investigation with the device, improper conduct of the study by the investigator, inability to obtain the number of subjects required by the protocol, etc. Reimbursements for reasonable expenses will be made if such an action is necessary.

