15.19 Deviations from study protocol

Any deviation from the study protocol should be notified to the sponsor, documented on study deviation forms and reported to the Ethics Committee as required.

Protocol deviations related to treatment compliance missed capsule, capsule taken on a non-capsule administration day, etc.) will not be declared on the protocol deviation form accessible via the **EDC** (Electronic Data Capture). Protocol deviations related to treatment compliance will be

monitored and declared by the Sponsor, CRO and sites using a platform external to the EDC. This external platform will use the information transmitted from the base units about activations (base unit serial number, date and time of activation, success/failure) as a basis to monitor treatment compliance.

Additional information transmitted by the subject from the eDiary about number of capsules taken out of the blister and swallowed for each day, as well as direct information given by the subject to the study coordinator by phone, email or SMS, will be used by the Sponsor and CRO to make a final decision about treatment compliance, for each day of treatment, for all subjects.

A final list of protocol deviations related to treatment compliance will be issued at the end of the study, from the external platform, and signed by the site. This list will be considered equivalent as protocol deviations forms. The site will not manually enter these protocol deviations in the EDC.

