17.9.8 Handling of Missing Data

Subjects with less than 6 weeks of diary data will be considered as failures for the CSBM and SBM success rates, as the primary imputation method for missing data.

Additional sensitivity analysis of the primary end-point will be performed to assess the impact of missing data on the study outcome using possible imputation methods for binary data:

- Multiple imputation for binary data.
- Observed Data: Use only subjects with 8 weeks of non-missing diary data and who did not withdraw early from study.
- Best Case Scenario: Assume all subjects with missing data in study group are successes; Assume all subjects in the placebo group with missing data are failures.
- Worst Case Scenario: Assume all subjects with missing data in study group are failures; Assume all subjects in the placebo group with missing data are successes.

In addition, for missing diary day, the number of bowel movement will be imputed to "0", and the intake of rescue medicine to "No". For the time to first SBM analysis, subjects with no known SBM will be considered left censored.

For the analyses of the other endpoints, no imputations for missing values will be performed.

Doc No: 280CLD

Rev: 01 Date: 24 May 2021

Page 75 of 103

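### Section 28 has no status between taking capsules and leaving the study, so a removal decision without a criterion can settle a subject's primary outcome

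*Combined protocol and SAP*

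**What the plan says.** Section 28 lists the reasons for early termination. Item 4 is "Non-compliance with medical device administration or study procedures as determined by the sponsor". No number of missed capsules or diary days is attached to it. Item 5 is "Change in subject's condition", with neither a criterion nor a decision-maker. The text above the list also covers non-compliance, serious adverse events and other medical problems, and for the last of these it reads: "in the opinion of the investigator, warrants discontinuation from the study for the safety of the subject, may necessitate discontinuing a subject".

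The only procedure after discontinuation is an exit visit: "Site staff should set an early termination visit as soon as they become aware of subject's discontinuation". Its content is then listed: "During this visit, any remaining study supplies should be collected and accountability should be conducted if applicable". An end-of-study form and other relevant information, such as adverse events, complete it. The Synopsis has the eDiary run daily to the end of the study, and no section says what happens to it after an exit.

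Two other sections bear on who decides. Section 22 states: "The investigator may withdraw a subject if, in his clinical judgment, it is in the best interest of the subject", and extends this to a subject who cannot follow the protocol. Section 15.19 says that base-unit, eDiary and contact information "will be used by the Sponsor and CRO to make a final decision about treatment compliance" for every treatment day.

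On scoring, 17.9.8 states: "Subjects with less than 6 weeks of diary data will be considered as failures for the CSBM and SBM success rates". It also sets bowel movements on a missing diary day to zero. Section 17.8.3 makes subjects with fewer than 2 valid diary weeks non-evaluable in the mITT set, which 17.8.5 makes the main efficacy set.

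**The concern.** Both primary endpoints, and the ranked secondary endpoints, depend on the daily eDiary. A subject who stops capsules could still keep a diary, but the protocol has no place for that subject: stopping and leaving are the same event. Two subjects with the same missed capsules and the same bowel response can therefore be classified differently, one on eight weeks of diary and the other on a record cut short by a judgement with no stated criterion.

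The loss is avoidable, because the outcome could be observed at little cost. In an arm of 51, each would-be responder scored as a failure moves the success rate by 1/51 = 2.0 points. For straining, stool consistency and bloating, 17.9.8 plans no imputation, so an exited subject could contribute at most the days before exit.

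**Working it through.** **Step 1. Scoring by time of removal, assuming the diary stops at exit.**

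| Diary weeks at exit | Result | Source |
|---|---|---|
| Under 2 valid weeks | Non-evaluable in mITT, not scored there | 17.8.3, 17.8.5 |
| 2 to under 6 | Failure on both primary endpoints | 17.2.1, 17.9.8 |
| 6 or 7 | Not automatic; later weeks count as zero, so 6 of 6 or 6 of 7 weeks must respond | 17.2.1, 17.9.8 |

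For illustration, assume a weekly response probability of 0.85 with independent weeks. The chance of success (at least 6 responding weeks) is:
- retained for 8 weeks: 89%;
- removed with 2 to under 6 weeks: 0%;
- removed after week 6: 0.85^6 = 38%;
- removed after week 7: 72%.

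**Step 2. The plan's own figure.** Inputs from 17.4: 12% vs 40%, two-sided 2.5% per endpoint, 46 per arm. The normal-approximation power, without continuity correction, is

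Φ{ (|p2 − p1|√n − z√[2p̄(1 − p̄)]) / √[p1(1 − p1) + p2(1 − p2)] }, with z = 2.2414 and p̄ the mean of the two rates.

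At n = 46 this gives 80.7%, and 46 is the smallest n per arm that reaches 80%. The plan's figure reproduces.

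**Step 3. The same formula at 51 per arm, with removals scored as failures.** Assume that 12% and 40% apply to retained subjects, that every removal occurs with under 6 diary weeks and is scored as a failure, and that none is replaced. A removal share d multiplies each rate by (1 − d).

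- d = 0: (0.28 × √51 − 2.2414 × √0.3848) / √0.3456 = 0.6092 / 0.5879 = 1.036, power 85.0%.
- d = 5% in each arm: 38% vs 11.4%, difference 26.6 points, power 82.1%.
- d = 10% in each arm: 40% × 0.9 = 36% and 12% × 0.9 = 10.8%, difference 25.2 points, power 78.8%.

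The removal shares are assumptions. The documents give only a total drop-out allowance of 10%.

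**Step 4. When it becomes bias.** With equal removal shares and no true effect, the arms keep equal expected success rates. If removals differ by arm, they do not. By exact enumeration at 51 per arm, with a true rate of 40% in both arms, the chance of a result favouring active at the two-sided 2.5% level is 1.2% with no removals and 3.3% if 10% are removed from placebo only. With a true rate of 12% in both arms, the figures are 1.1% and 1.7%. Nothing in the documents predicts such an imbalance.

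**The case against.** The strongest reply is that failure scoring is a pre-specified non-responder rule and that a subject with under 6 diary weeks cannot meet a 6-of-8 endpoint anyway. That is correct, and the rule itself is not an error. What remains is that an undefined judgement can trigger it while outcome data that could be collected are not.

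The second reply concerns size, and most of it stands. Step 3 assigns the whole 10% drop-out allowance to removals, although consent withdrawal and loss to follow-up would occur regardless. The planned power is 80%, so 78.8% is close to plan. Section 28 also allows exits to be replaced, up to 10%; at an assumed 56 per arm, 10% removed in each arm gives 82.9%. The figures are therefore an upper bound.

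Third, 17.9.8 plans multiple imputation, observed-data, best-case and worst-case analyses. These impute, drop or bound the missing outcomes. They do not recover them, and none separates sponsor-decided removal from other causes.

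Several stronger readings are tempting but unsupported:
- *The sponsor may remove a subject for a change in condition.* Sponsor determination is written only into item 4; item 5 names nobody, and medical removals rest on the investigator's opinion.
- *The protocol stops the diary at exit.* It is silent. Stopping is a reasonable inference, though section 22 asks that attempts be made to complete examinations.
- *Every removed subject is scored a failure.* This holds only in the middle timing band of Step 1.
- *Sponsor staff judge compliance unblinded.* Sections 15.13 and 17.7 name only subjects and evaluators as blinded, but 15.14 restricts unblinded information and has unblinding reported to the sponsor, which suggests that the sponsor is not routinely unblinded. Section 15.19 concerns a deviation list and does not mention removal.
- *Sections 22 and 28 contradict each other on who decides.* Both are permissive and can apply together. The division of authority is unclear rather than inconsistent.

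**Conclusion.** The point holds as a gap in design and wording. Section 28 equates stopping capsules with leaving the study, gives no criterion for sponsor-determined non-compliance, and makes no provision for diary data after exit. If the diary does stop, the time of removal decides whether a subject is left out of the main analysis, failed, or scored with zeros.

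The expected consequence is modest dilution: at most a fall in power from 85.0% to 78.8% at 51 per arm under the assumptions in Step 3, and to 82.1% with 5% per arm. A reader might infer that the primary comparison is biased. The documents do not show that; it would require removals to differ by arm. The label is a cheap improvement.

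**What to change.** In section 28, separate stopping capsules from ending data collection. Ask subjects who stop capsules, and who have not withdrawn consent, to keep the daily eDiary to the end of week 8 and to attend the planned Visit 4 with PAC-QOL. Set the item 4 non-compliance criterion in advance, and state that the sponsor and CRO staff who apply it are blind to arm. Reconcile sections 22 and 28 on who decides. The clinical grounds for stopping capsules, and removal for a subject's welfare, stay with the study's own rules.

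The cost is protocol wording plus a few more weeks of eDiary reminders for a small number of subjects. No visit is added beyond Visit 4.
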